Effects of Er:YAG Photobiomodulation Therapy on Wound Healing of
Human Palatal Mucosa After Connective Tissue Graft Harvesting:
A Pilot Study

NCT03741062

October 16, 2020

STUDY PROTOCOL

Participants

Patients of the Graduate Periodontics Clinic at the University of Manitoba who require a subepithelial connective tissue graft (SECTG) utilizing autogenous donor tissue harvested from the palate, during the time period from Fall 2018 to Spring 2020, and who sign the consent form will be eligible to participate. Patients will receive initial periodontal examination and treatment if necessary. Patients must be classified as ASA I or ASA II according to the American Society of Anesthesiologists and demonstrate both a Full Mouth Plaque Score (FMPS) and a Full Mouth Bleeding Score (FMBS) <20% to be included in the study. Patients with any contraindications for periodontal surgery, who are currently taking anticoagulants or corticosteroids, or who smoke >10 cigarettes/day will be excluded from the study.

Clinical Methodology

A computerized randomization program will assign participants to one of two groups. Patients will be block-randomized to ensure a balance between all the operators. Both groups will undergo SECTG surgery for root coverage utilizing an autogenous graft obtained from the patient's palate. Details regarding the preparation of the recipient site and the specific root coverage technique will not be dictated by the experimental protocol as they will have no effect on the outcomes being measured. The palate is anesthetized with 2% lidocaine (1:100000 epinephrine) by greater palatine nerve block, nasopalatine nerve block, and local infiltration as needed, ensuring not to inject anesthetic into the graft tissue. Prior to harvesting the graft, the

thickness of the palatal tissue at the donor site will be measured via transgingival probing (or ultrasound device). Graft tissue will be harvested according to the Single-Incision Technique described by Hurzeler.

Surgical Technique: The donor area of the palate is located between the root of the canine and the palatal root of the first molar. Its lateral border is positioned approximately 2 mm from the gingival margin and its medial border is dictated by the position of the palatal neurovascular bundle which can be found 7, 12, or 17 mm from the cemento-enamel junction of the correspondent teeth, depending on whether the palatal vault is shallow, average, or high, respectively. A single horizontal incision, whose length corresponds to the required length of the graft, is made at 90° to the underlying bone approximately 2 mm from the gingival margin with a #15 blade. The blade is then angled at approximately 135° to the bone and a split-thickness dissection is started within that first incision, towards the median of the palate. As the incision is advanced, the angle of the scalpel is further flattened until it is nearly parallel to the bone surface. Elevation of the overlying tissue should be avoided to reduce the risk of perforation while making this incision. Split-thickness dissection continues until the necessary dimensions of the graft are obtained, ideally maintaining 1.0-1.5 mm of overlying tissue. The SECTG is separated from the surrounding tissue via incisions to the bone surface at the mesial, distal, and medial borders of the graft. The graft is detached from the bone with a periosteal elevator and placed on a saline-soaked gauze until it is transferred to the recipient site.

The length, width, and thickness of the graft, the thickness of the remaining palatal tissue, and the length of the palatal incision will be measured with digital calipers to the nearest 0.1 mm. Palatal incisions will be closed with cyanoacrylate. Immediately following completion of the

surgical procedure, Group A will receive PBM treatment of the donor site with Er:YAG laser according to the parameters shown to induce maximal proliferation of human gingival fibroblasts (Energy Setting: 80 mJ, Pulse Rate: 25 Hz, Duration: 30 s). Group B will receive sham treatment with the laser unit turned off.

During all sessions of laser treatment, the manufacturer-recommended safety precautions will be stringently adhered to. The clinician, patient, and any other individuals inside the operatory must always wear Laser Safety Glasses designated for use with Er:YAG lasers. Whenever possible, the individuals present within the operatory will be limited to the patient and those directly involved with the procedure (i.e. the clinician and assistant). The activated laser should never be directed anywhere other than the intended site of treatment. If the operator, patient, or anyone else in the operatory suspects they may have incurred damage to their eyes or skin, they should be examined by a dermatologist and/or ophthalmologist. A sign of notification that laser surgery is in progress will be placed at the entrance of the operatory. The Er:YAG laser is not intended for use on patients who have a pacemaker or implantable cardioverter defibrillator, however these patients would not fit the inclusion criteria of ASA I and ASA II classification and thus would already be precluded from participation in the study. The laser unit should not be used in the presence of combustible anesthetic or an elevated concentration of oxygen. If the administration of oxygen is absolutely necessary, it will be ensured that there is no leakage of oxygen and the oxygen delivery tube will be protected with a non-combustible cuff.

Both groups will receive 2 g of Amoxicillin (or 600 mg of Clindamycin in cases of penicillin allergy) and 400 mg of Ibuprofen immediately following surgery, in addition to the standard post-operative instructions given to patients at the U of M Graduate Periodontics Clinic. This includes

application of an ice pack for the first 24 hours, BID rinsing with 0.12% Chlorhexidine, avoiding the surgical sites during oral hygiene, avoiding hot foods and liquids, avoiding hard and crunchy foods for 24 hours after surgery, refraining from smoking for two weeks and avoiding sucking on straws or spitting. Patients will also be provided with a bag of 30 200-mg Ibuprofen tablets. They will be given a Visual Analogue Scale (VAS) questionnaire to rate their post-operative pain from 0 to 10 for each night of the first post-operative week.

At the one-week post-operative appointment, the participants will return their VAS questionnaires and any remaining Ibuprofen tablets. They will be asked to fill out a modified Oral Impacts on Daily Performance (OIDP) questionnaire to assess the effect of the palatal wound on their oral-health related quality of life during the first post-operative week. A clinician who did not perform the surgery and is blinded to which treatment group the patient belongs will assess the donor site at the one- and two-week post-operative appointments according to a modified early-wound healing index (MEHI) proposed by Fickl (a variation of the EHI originally conceived by Wachtel) as well as the healing index (HI) of Landry, Turnbull and Howley. Participants will return for a six-week post-operative appointment, during which tissue thickness at the donor site will be measured via bone sounding and a histological specimen will be harvested with a tissue punch. Tissue samples will immediately be submerged in a solution of 10% neutral buffered formalin. Clinical photographs will be taken at all appointments.

Risks

There is the risk in both the test and control groups of post-operative complications that are associated with any periodontal surgery including intraoral pain or discomfort, bleeding,

infection, swelling and bruising. There is also a risk that the desired outcome, either partial or complete root coverage (depending on the severity and classification of the initial recession defect), may not be achieved by the surgical procedure.

Potential Benefits

If Er:YAG photobiomodulation of the palatal donor site results in improved and/or faster healing of the tissue or less post-operative discomfort, then patients requiring SETGs will benefit from a shorter and more pleasant healing period following their surgery. Also, as the effects of Er:YAG PBM on healing have never been investigated in human studies, the information gained from this study would help direct future research on this topic.

Consent Process

Patients of the Graduate Periodontics Clinic at the University of Manitoba who require SECTG and who meet the eligibility requirements will be asked personally if they would like to be a part of the project. After being given a brief description of the research, if the patient is interested, they will be provided a written summary of the study and a consent form to sign if they would like to take part.

Data Security

All data will be recorded based on the subject's assigned number after they have agreed to participate and have signed the consent form. Their names and contact information will be stored in a secure, locked location at the U of M Graduate Periodontics Clinic. Findings from the

study may be published or presented in a public forum. Participants' names will not be used and no identifying details revealed.

STATISTICAL ANALYSIS PLAN

The study will be blinded at the level of data collection and data assessment. The primary outcome for this study is the patients' post-operative discomfort from the palatal donor site during the first week following surgery. This is assessed by VAS scores and analgesic consumption. Friedman's two-way ANOVA test will compare the change in VAS scores over time within each treatment group. Mann-Whitney U test will compare the difference in VAS scores between the two groups at each time point as well as the differences in total analgesic use between the two groups. The secondary outcomes are healing of the donor site and the palatal wound's effect on the patients' OHQoL. Healing is assessed by MEHI and HI scores and by tissue thickness. Wilcoxon Signed Ranks test will compare the change in MEHI and HI scores from week one to week two within each treatment group. Mann-Whitney U test will compare the differences in MEHI and HI scores between the treatment groups as well as the differences in tissue thickness at six weeks post-operatively between the groups. OHQoL is assessed by OIDP scores. The differences in OIDP scores between treatment groups is compared with Mann-Whitney U test. The level of significance is $p \leq 0.05$. IBM SPSS Statistics for Windows (Version 25.0) is used for analysis.

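### Wound dimensions are measured before laser or sham and randomisation is blocked by operator, but the primary pain comparisons use neither: a valid test that may be less precise than it could be

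*Combined protocol and SAP*

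**What the plan says.** **Measurements.** Under Clinical Methodology, before the graft is taken, the "thickness of the palatal tissue at the donor site will be measured via transgingival probing (or ultrasound device"). Under Surgical Technique, after harvest, "The length, width, and thickness of the graft" are recorded to 0.1 mm, and in the same sentence "the thickness of the remaining palatal tissue, and the length of the palatal incision will be measured with digital calipers". The incision is then closed, and only when surgery is over is the treatment given: "surgical procedure, Group A will receive PBM treatment of the donor site with Er:YAG laser", with sham for Group B.

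**Randomisation.** Clinical Methodology describes two groups, with blocks used to keep operators balanced between them. Nothing balances wound size.

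**Analysis.** The SAP states: "The primary outcome for this study is the patients' post-operative discomfort from the palatal donor site during the first week following surgery". It is assessed by VAS and analgesic consumption. For the comparison between groups, "Mann-Whitney U test will compare the difference in VAS scores between the two groups at each time point". The same unadjusted test is applied to the tablet counts: "as well as the differences in total analgesic use between the two groups". Within groups, "Friedman's two-way ANOVA test will compare the change in VAS scores over time within each treatment group". No analysis of any outcome has a covariate or a stratum, and the SAP does not mention the caliper measurements.

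**Not stated.** The documents give no sample size, number of operators, target difference, VAS standard deviation, or correlation between wound size and pain.

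**The concern.** The primary outcome is pain from the palatal wound, and the plan measures that wound closely before treatment. Wound size should differ between patients. Incision length and extent of dissection follow the graft that the recipient site needs, the root-coverage technique is left open, and several operators take part. If a larger wound hurts more, part of the spread in VAS and tablet counts could be explained by data already collected. An unadjusted comparison leaves that part in the noise.

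Operator raises a similar question. The design balances on it but the analysis ignores it. If operators differ in the pain that follows their surgery, the analysis does not recover the precision that the blocking was meant to give.

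In a small trial the arms can also differ in wound size by chance. The SAP plans no adjusted analysis that would help a reader interpret such a result.

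**Working it through.** The plan has no power figure to reproduce, so every figure below is conditional on assumptions: 1:1 allocation, two-sided 0.05, a standardised effect of 0.8, and r between wound size and VAS from 0 to 0.5.

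**1. Precision from one covariate.** Adjustment multiplies residual variance by 1 − r². In a small sample, estimating the slope costs something. The squared confidence-interval width, adjusted over unadjusted, is approximately

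(1 − r²) × (1 + 1/(N − 4)) × (t on N − 3 df / t on N − 2 df)²

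This is the linear-model formula, used here as a guide to the rank version.

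| Total N | r = 0 | r = 0.2 | r = 0.3 | r = 0.5 | Break-even r |
|---|---|---|---|---|---|
| 16 | 1.099 | 1.055 | 1.000 | 0.824 | 0.30 |
| 20 | 1.072 | 1.029 | 0.975 | 0.804 | 0.26 |
| 30 | 1.042 | 1.000 | 0.948 | 0.781 | 0.20 |
| 40 | 1.030 | 0.988 | 0.937 | 0.772 | 0.17 |

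The inverse of each ratio gives the equivalent gain in patients:
- N = 20: 1/0.975 = 1.026 (about 3%) at r = 0.3, and 1/0.804 = 1.244 (24%) at r = 0.5.
- N = 30: 1/0.948 = 1.055 (about 6%) at r = 0.3, and 1/0.781 = 1.280 (28%) at r = 0.5.

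**2. Power by simulation.** There were 4,000 runs per setting, with VAS from 0 to 10 in half-unit steps. The Mann-Whitney test was compared with a regression of ranked VAS on arm and the ranked covariate, with no operator term.

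| Per arm | r | Mann-Whitney | Rank ANCOVA | Gain (points) |
|---|---|---|---|---|
| 10 | 0 | 35.2% | 36.3% | 1.1 |
| 10 | 0.3 | 35.1% | 39.1% | 4.0 |
| 10 | 0.5 | 35.9% | 44.9% | 9.0 |
| 15 | 0 | 53.8% | 54.2% | 0.4 |
| 15 | 0.3 | 52.5% | 56.4% | 3.9 |
| 15 | 0.5 | 52.6% | 64.2% | 11.6 |
| 20 | 0 | 67.2% | 66.8% | −0.4 |
| 20 | 0.3 | 66.5% | 70.3% | 3.8 |
| 20 | 0.5 | 66.4% | 76.7% | 10.3 |

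The standard error of one power estimate near 54% is √(0.54 × 0.46/4000) = 0.8 points. A repeat at 15 per arm and r = 0.5 gave 53% against 63%, so "about 10" is a fair summary. Type I error of the rank ANCOVA was 4.3-5.6%.

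**3. Operator strata.** A further simulation assumed five operators and 10 to 15 per arm. Adding operator gained 5 to 9 points more when operators affected pain and lost about 1 to 2 when they did not. Adjusted type I error was about 3-6%. The documents give neither the number of operators nor any operator effect.

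**4. Chance imbalance.** The arm difference in mean wound size, in SD units, has standard error √(2/n). The chance that it exceeds 0.5 SD in either direction is:
- n = 10: 0.5/0.447 = 1.12, so 26%.
- n = 15: 0.5/0.365 = 1.37, so 17%.
- n = 20: 0.5/0.316 = 1.58, so 11%.

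Among simulated null trials with such an imbalance, the unadjusted test rejected in 8%, 11% and 13% respectively at r = 0.5, and in 5-7% at r = 0.3. The rank ANCOVA stayed near 5% at r = 0.5. Over all randomisations the unadjusted test keeps its nominal level.

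**The case against.** The strongest reply is that this is a preference about efficiency and not an error. That stands. A reader might infer that leaving out wound size biases the pain comparison or invalidates the test. It does neither, because randomisation protects the comparison and the test's error rate already allows for chance imbalance.

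A reader might also take it as shown that the plan wastes precision. The documents give neither r nor N, and below the break-even r adjustment costs a little precision. The large-sample formula 1/(1 − r²) would suggest 10% to 33% more patients for r = 0.3 to 0.5. That is too generous for a pilot, and the small-sample figures above should be used. Even with adjustment, 15 per arm would reach only about 56% power at r = 0.3.

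The covariate's status is a further objection, and it stands as a condition. Measurement before the laser does not by itself make wound size a baseline variable. The surgeon sets graft size during harvest, and the documents do not say when the surgeon learns the allocation. The SAP claims blinding for data collection and assessment only. If allocation is known at harvest, wound size could be affected by it.

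Lastly, nothing in the documents shows which wound measure best predicts pain. Naming one in advance prevents selection by result but does not make it prognostic. This limits the expected gain and is not a reason to leave the choice open.

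**Conclusion.** The point holds as a recommendation on efficiency. Wound measurements taken before treatment, and the factor on which randomisation is blocked, are both left out of the primary between-group comparisons. The planned test is sound.

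The likely benefit of the wound covariate runs from nothing to moderate. The upper end needs r near 0.5, and a clear gain in a trial of 20 to 30 patients needs r above roughly 0.2 to 0.3. Operator could add more or cost a little, depending on whether operators differ. That the trial is small is inferred from its description as a pilot. Treating wound size as baseline requires that allocation was concealed until it was recorded.

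**What to change.** In the SAP:

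1. Make the between-group VAS and total analgesic comparisons rank analyses of covariance, with one prespecified wound measure (for example graft area, length × width) and operator as stratum.
2. Keep the unadjusted Mann-Whitney test as a sensitivity analysis.
3. State that allocation was concealed from the surgeon until the wound measurements were recorded. If it was not, adjust for operator only, or also for pre-harvest palatal thickness if that was measured before allocation was known.
4. Fix the covariate before outcomes are seen by arm. The document is dated October 2020 and its recruitment period ends in spring 2020. If outcomes have already been seen by arm, label the adjusted analysis post hoc.

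**Cost.** No new data, some SAP wording and modest analysis work. The statistical cost is one degree of freedom for the covariate plus the number of operators minus one for the strata. With five operators (assumed) and 30 patients, that is 1 + 4 = 5 of the 28 error degrees of freedom in an unadjusted two-group comparison. The SAP should state the number of operators so that this cost can be judged.

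### Total analgesic use is one of two primary measures, but the only data described for it are returned study ibuprofen tablets, so patients who take other analgesics would rank as low users

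*Combined protocol and SAP*

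**What the plan says.** The SAP states: "The primary outcome for this study is the patients' post-operative discomfort from the palatal donor site during the first week following surgery". It continues: "This is assessed by VAS scores and analgesic consumption". VAS is compared between arms at each time point by Mann-Whitney U, and the same test is applied to "the differences in total analgesic use between the two groups".

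The data behind the second measure are described under Clinical Methodology. Both arms receive "400 mg of Ibuprofen immediately following surgery". For home use: "Patients will also be provided with a bag of 30 200-mg Ibuprofen tablets". At the one-week visit, "the participants will return their VAS questionnaires and any remaining Ibuprofen tablets". The take-home form asks patients "to rate their post-operative pain from 0 to 10 for each night of the first post-operative week"; no medication entry is mentioned.

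The documents do not define total analgesic use. They describe no medication diary and no question about other pain medicines. They give no rule that permits, forbids or converts other analgesics, and none for an empty or unreturned bag.

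**The concern.** The SAP names a broad quantity, all analgesic use, while the protocol describes data on one product from one supply. The natural calculation is 30 minus the tablets returned. On that calculation, anyone who takes a different analgesic or ibuprofen from their own cupboard returns more study tablets and is ranked as a lighter user than they were. A patient who takes no study ibuprofen is scored zero, whatever else was taken.

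The decision to take something else is likely to depend on pain, so the missing information is unlikely to be unrelated to the outcome. The two primary measures are also linked: an unrecorded drug can lower that night's VAS as well as the tablet count, moving both in the same misleading direction. At stake is the arm comparison on one of the two primary measures, and the usefulness of this pilot's estimate for later research.

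**Working it through.** The plan states no sample size, effect size or power, so there is no figure of its own to reproduce. The check has three parts.

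**1. The supply (document figures).**
- Total: 30 × 200 mg = 6000 mg.
- Per day over seven days: 30 / 7 = 4.29 tablets, or 6000 / 7 = 857 mg.
- At 4 tablets a day the week needs 7 × 4 = 28, and nothing is lost.
- At 5, 6 or 8 a day it needs 35, 42 or 56, so 5, 12 or 26 tablets lie beyond the count.
- The 400 mg given in clinic is the same in both arms and does not alter their ranking.

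**2. Effect of the 30-tablet limit on the planned test.** The recorded value is min(x, 30). This keeps the order of all patients and only creates ties above 30. A patient who empties the bag still ranks among the heaviest users.

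Illustration, all inputs assumed: 20 per arm, negative-binomial weekly counts with shape 3, two-sided Mann-Whitney at 0.05 (the SAP does not state sidedness).

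| Assumed means | Power, full capture | Power, limit of 30 only |
|---|---|---|
| 14 v 24 | about 69% | 67–68% |
| 20 v 30 | 46–47% | 42–43% |

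The difference in means shrinks more (from 10 tablets to 6.8 and 4.8), but the SAP does not test means.

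**3. Effect of unrecorded analgesics.** Same model, with a switcher assumed to replace 70% of tablets by something unrecorded. If 25% of each arm switch at random, the expected recorded share is 1 − 0.25 × 0.70 = 0.825. A true difference of 10 tablets then becomes 8.25 before the limit is applied. Power with the limit also applied:

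| Who switches (assumed) | 14 v 24 | 20 v 30 |
|---|---|---|
| Random 25% of each arm | about 49% | about 30% |
| Half of those above 20 tablets | about 32% | about 18% |
| Exactly the heaviest 25% of each arm | 73–85% | 39–63% |

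The first two rows apply the limit after switching. Applying it before gives lower figures, about 44% for random switching and 23% for use-related switching at 14 v 24. The last row spans both orders. A fixed threshold such as 20 tablets catches more patients in the heavier-using arm. Taking exactly the top quarter of each arm removes the same number from both, so the ordering between arms can survive or even sharpen. With only 5% switching at random, power at 14 v 24 is about 63–65%.

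**Unequal switching, no true difference.** Assume a true mean of 16 tablets in both arms (gamma, SD 10), 10% v 30% switching, and switchers recording 25% of true use. The expected artificial gap is 16 × 0.75 × (0.30 − 0.10) = 2.4 tablets, or about 2.2 in simulation with the limit. The arm that switches more appears to use less. The rejection rate is about 11% with 15 per arm (9–14% for 10 to 20 per arm), against a nominal 5%. The negative-binomial model gives about 12%.

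**The case against.** A reader might infer that patients who switch look pain-free. The documents do not support that: every patient rates pain nightly and VAS is tested separately, so a switcher looks like a low ibuprofen user and no more.

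A reader might also take the 30-tablet limit as the main defect. It matters only above about 4.3 tablets a day and barely touches a rank test.

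That the measure counts only returned tablets is inferred from silence. The listed post-operative instructions may be partial and the VAS form is not reproduced, so a medication question could exist. What can be said is that no other source is described and that the measure is undefined.

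The strongest objection is to the size. The power figures rest on assumed sample size, means, distribution and switching pattern, and one plausible-looking pattern shows no loss at 14 v 24. Sham treatment and blinded data collection make similar under-recording in both arms plausible, in which case the usual cost is power rather than a false signal. This is also a self-described pilot.

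All of this limits what can be claimed about magnitude. It does not remove the mismatch between the quantity the SAP tests and the data the protocol describes.

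**Conclusion.** The point holds as a measurement gap in one of the two primary measures. Followed as written, the plan ranks users of other analgesics, or of their own ibuprofen, as low users, and it leaves the compared quantity undefined.

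The size cannot be fixed from the documents. Under the assumptions above (20 per arm, means 14 v 24), unrecorded use typically takes power from about 69% to 32–49%, but size and even direction depend on who switches. Switching of 10% v 30% with no true difference raises the rejection rate to about 11–13%. These figures illustrate the mechanism and do not estimate this trial's loss. The tablet limit is a minor part. The change is a cheap improvement that should be made.

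**What to change.** **Data capture.** Add two columns to the nightly VAS sheet: study ibuprofen tablets taken that day, and any other pain medicine (name, strength, number). Keep the returned-tablet count as a check.

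**SAP.** Define the compared outcome so that it covers all recorded analgesics, for example a total in a common unit by a prespecified conversion, compared by Mann-Whitney U. Adding only the patient's own ibuprofen would not be enough, because someone who changes to a different drug would still score low. Add a sensitivity analysis that ranks users of other analgesics among the highest users, report use of any other analgesic (yes/no) by arm, and state how an unreturned bag is handled.

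**If collection is complete.** The document is dated October 2020 and the stated recruitment window ends in Spring 2020, so the sheet may no longer be changeable. In that case, rename the measure as study ibuprofen tablets used and limit the conclusion to that.

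**Cost.** One revised page, a short SAP definition, slightly more for patients to write and a little more analysis. Supply and treatment are unchanged.

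### Beyond pain, analgesic use, healing measures and OIDP, the plan does not collect or report by arm the complications the protocol itself names

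*Combined protocol and SAP*

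**What the plan says.** **Named risks.** The Risks section says both groups face "post-operative complications that are associated with any periodontal surgery including intraoral pain or discomfort, bleeding", followed by "infection, swelling and bruising". It attributes all of these to the surgery and none to the laser.

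**Laser injury.** The safety paragraph under Clinical Methodology says that if anyone in the operatory "suspects they may have incurred damage to their eyes or skin, they should be examined by a dermatologist and/or ophthalmologist". It does not say that the event or the result of the examination enters the trial data.

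**Novelty.** Potential Benefits states that "as the effects of Er:YAG PBM on healing have never been investigated in human studies" and that the results should guide later research.

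**Design.** "A computerized randomization program will assign participants to one of two groups", and "Group B will receive sham treatment with the laser unit turned off".

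**Data collected after surgery.** Under Clinical Methodology these are a nightly VAS form for pain in the first week, returned ibuprofen tablets and an OIDP questionnaire at one week, MEHI and HI scores by a blinded clinician at one and two weeks, tissue thickness and a biopsy at six weeks, and photographs at every appointment.

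**Analysis.** The SAP's primary outcome is first-week donor-site discomfort (VAS and analgesic use). It continues "The secondary outcomes are healing of the donor site" and the wound's effect on quality of life. No adverse-event or complication outcome appears.

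**The concern.** The protocol names specific complications and foresees one kind of laser injury, but nothing in the visit schedule asks about either and nothing in the SAP tabulates them. This gap cannot be closed at the analysis stage. A bleed at home on the second night that has settled by the one-week visit need not leave a trace in a pain score, a healing index or a photograph.

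At stake is a descriptive account of complications by arm. The protocol ties every listed complication to surgery, so whether the laser changes their frequency is open. The randomised sham arm is the right comparator for describing that, and without counts it goes unused. A later, larger trial would then have no complication rates from this pilot to plan with.

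**Working it through.** **1. Each named event against the plan.**

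| Event named in the protocol | Planned collection | Planned comparison by arm |
|---|---|---|
| Pain or discomfort | Nightly VAS, tablets returned | Yes, primary outcome |
| Bleeding | None specified | None |
| Infection | None specified | None |
| Swelling | None specified | None |
| Bruising | None specified | None |
| Suspected eye or skin damage | Referral only | None |

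One of the six is an outcome. MEHI, HI, tissue thickness and OIDP are also compared by arm and can move in the harmful direction. They are scores or thicknesses analysed by rank tests, which yield no event rate. The documents do not reproduce the items of MEHI or HI, so some overlap with bleeding or swelling is possible, but no complication count is planned from them. No reading or coding of the photographs is planned either.

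**2. What counts could deliver.** The plan states no sample size, complication rate or power, so there is no figure to reproduce. The following assumes 10, 15 or 20 patients per arm.

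If no events are recorded among n patients, the exact 95% upper limit on the true rate is
- one-sided: 1 − 0.05^(1/n)
- two-sided: 1 − 0.025^(1/n)

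| n per arm (assumed) | One-sided | Two-sided |
|---|---|---|
| 10 | 1 − 0.741 = 25.9% | 1 − 0.692 = 30.8% |
| 15 | 1 − 0.819 = 18.1% | 1 − 0.782 = 21.8% |
| 20 | 1 − 0.861 = 13.9% | 1 − 0.832 = 16.8% |

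The chance that an arm shows at least one event at true rate p is 1 − (1 − p)^n. For p = 10% this is 65%, 79% and 88% at n = 10, 15 and 20. For p = 5% it is 40%, 54% and 64%. Events of that frequency are therefore likely enough to occur to be worth writing down.

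**3. What counts could not deliver.** Exact power of a two-sided Fisher test at 0.05, with assumed rates:

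| n per arm (assumed) | 5% vs 20% | 10% vs 30% |
|---|---|---|
| 10 | 2% | 6% |
| 15 | 8% | 15% |
| 20 | 17% | 24% |

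By the usual normal approximation, 80% power would need 76 per arm for 5% vs 20% (88 with continuity correction) and 62 per arm for 10% vs 30% (72 with correction). A formal comparison is not a realistic aim for a small pilot; counts and intervals are.

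**The case against.** The strongest reply is that the trial already measures harm. Pain is the first complication under Risks and is the primary outcome. Healing and daily impact are compared by arm, and nothing restricts those tests to the favourable direction. This stands. A reader might infer that the trial has no harm outcome by arm, or can report benefit but not harm; the SAP contradicts both.

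The novelty statement is also narrow. A reader might take it to mean that the laser, or its safety, has never been examined in people. It concerns effects on healing only, and the same document describes a device with manufacturer precautions.

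Third, a small pilot could not show whether the laser causes complications even with perfect recording. The power figures confirm this, again at assumed sizes. It limits what the counts can support, but is no reason to collect none.

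Fourth, no case report form is shown and the index items are not listed, so it cannot be asserted that no clinic record would ever mention a complication. This is right. The supportable statement is that neither the protocol nor the SAP specifies eliciting, recording or reporting them.

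Finally, eye or skin injury is an incident that may affect staff as well as patients, and it already has a response. It differs in kind from a donor-site complication, and asking a blinded assessor about it could reveal allocation. This affects how it should be recorded, not whether it should be.

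**Conclusion.** The point holds in a limited form. Bleeding, infection, swelling, bruising and suspected laser eye or skin injury are foreseen by the protocol but are not planned to be elicited, recorded or reported by arm. The pilot would yield no complication counts for a use whose effect on healing it describes as unstudied in humans.

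With recording and zero events, an arm's rate could be bounded at about 31% to 17% (two-sided) or 26% to 14% (one-sided), on the assumption of 10 to 20 patients per arm. Without recording, the trial provides no bound from systematic data. The finding itself rests on the text and does not depend on the assumed sizes.

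**What to change.** **Collection**
- Add yes/no items for bleeding, swelling and bruising to the nightly VAS form used in week one, so that events at home do not rest on recall at the visit.
- Have the blinded clinician complete a short checklist (bleeding, infection, swelling, bruising, other) at the one- and two-week visits.
- Have whoever examines the donor site at six weeks complete the same checklist, unaware of allocation. The protocol names a blinded assessor only for weeks one and two; at six weeks there is only the SAP's general blinding statement.
- Have the treating staff record any suspected eye or skin injury on the treatment day, so that the question does not unblind the assessor.

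**SAP**
- Tabulate, by arm and event type, the number and percentage of patients affected, with exact two-sided 95% intervals, descriptively and without a test.
- State that the pilot cannot exclude moderate differences between arms.

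**Cost.** A slightly longer form and visit, and one extra table. All the visits already take place and no extra staff are needed.

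**If visits are already complete.** Recruitment was planned to end in spring 2020 and the document is dated October 2020, so this may apply. In that case, report by arm what the clinic records hold and state that complications were not systematically collected.
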